4.2. Exclusion Criteria

Subjects with any of the following characteristics/conditions will not be included in the study:

1. Has any clinically significant medical disorder, condition, or disease (including active or potentially recurrent non-AD dermatological conditions and known genetic dermatological conditions that overlap with AD, such as Netherton syndrome) or clinically significant physical examination finding at Screening that in the PI's or designee's opinion may interfere with study objectives (eg, expose subject to unacceptable risk by study participation, confound evaluation of treatment response or AEs, or interfere with subject's ability to complete the study).
2. Has unstable AD or any consistent requirement for high/strong potency or very high/very strong potency topical corticosteroids to manage AD signs and symptoms.
3. Has a history of angioedema or anaphylaxis.
4. Has a significant active systemic or localized infection, including known actively infected AD.
5. Has received any of the prohibited medications/therapies that may alter the course of AD without the required minimum washout (see [Section 5.8.1](#)) or anticipated concomitant use of the any of the prohibited medications/therapy (see [Section 5.8.2](#)).
6. Has any planned surgical or medical procedure that would overlap with study participation, from Screening through the end of study.
7. Has history of cancer within 5 years or has undergone treatment for any type of cancer (except squamous cell carcinoma, basal cell carcinoma, or carcinoma in situ of the skin, curatively treated with cryosurgery or surgical excision only).
8. Has a known sensitivity to any of the components of the investigational product.
9. Has participated in a previous crisaborole clinical study or had previous treatment with Crisaborole ointment, 2%, or other topical or oral PDE-4 inhibitors.
10. Investigator site staff members directly involved in the conduct of the study and their family members, site staff members otherwise supervised by the investigator, or subjects who are Pfizer employees, including their family members, directly involved in the conduct of the study.

11. Participation in other studies involving investigational drug(s) within 30 days prior to study entry and/or during study participation.
12. Other acute or chronic medical or psychiatric condition including history of or active suicidal ideation or behavior or laboratory abnormality that may increase the risk associated with study participation or investigational product administration or may interfere with the interpretation of study results and, in the judgment of the investigator, would make the subject inappropriate for entry into this study including the following:
 - For subjects 7-11 years of age, suicidal ideation associated with actual intent and a method or plan in the past 6 months: “Yes” answers on items 4 or 5 of the Columbia suicide severity rating scale (C-SSRS) or a previous history of suicidal behaviors in their lifetime: “Yes” answer to any of the suicidal behavior items of the C-SSRS.

- For subjects ≥ 12 years of age, suicidal ideation associated with actual intent and a method or plan in the past year: “Yes” answers on items 4 or 5 of the C-SSRS or a previous history of suicidal behaviors in the past 5 years: “Yes” answer (for events that occurred in the past 5 years) to any of the suicidal behavior items of the C-SSRS
 - For younger subjects under 7 years of age, subject has suicidal ideation and behavior risks assessed clinically and in consultation with their parents/caregivers
13. Pregnant female subjects; breastfeeding female subjects; and female subjects of childbearing potential who are unwilling or unable to use an appropriate method of contraception as outlined in this protocol for the duration of the study and for at least 28 days after the last dose of investigational product.

4.3. Randomization Criteria

Subject will be randomized into the study provided that the subject [or parent(s)/legal guardian] has signed an informed consent (or assent, if applicable) document to participate in the study, and the subject has undergone all screening procedures, and meets all inclusion and exclusion criteria for participation in the study at the baseline visit. A centralized computer generated randomization schedule will be used to assign subjects to the treatment groups. Subjects will be randomized in a 2:1 ratio to one of the 2 parallel treatment groups (Crisaborole ointment, 2% BID or Crisaborole placebo vehicle ointment BID).

Subjects will be assigned a subject identification number in the order of their screening for the study. The identifying number will be retained throughout the study.

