3. STUDY DESIGN

This is a Phase 3, multicenter, randomized, double-blind, vehicle-controlled study to evaluate the efficacy and safety of crisaborole ointment, 2% in Chinese and Japanese pediatric and

[figure not shown]
adult subjects (ages 2 years and older) with mild to moderate atopic dermatitis involving at least 5% treatable BSA.

A total of approximately 384 subjects (approximately 50% for age ≥ 12 years old and approximately 50% for age < 12 years old) will be enrolled in the study from multiple sites in China and Japan. Following the screening period (up to 35 days prior to Baseline/Day 1), eligible subjects will be randomized at the Baseline/Day 1 visit in a 2:1 ratio to one of 2 treatment groups (crisaborole ointment, 2% BID; vehicle BID, respectively), the investigational product will be applied BID for 28 days to the Treatable BSA identified at Baseline/Day 1 and new AD lesions that appear after the Baseline/Day 1. The primary efficacy endpoint, percent change from baseline in EASI total score, will be assessed at Day 29.

Scheduled study visits for all subjects will occur at Screening, Baseline/Day 1, Day 8, Day 15, Day 22, Day 29 (End of treatment/Early termination). A follow up telephone call will be made by site staff to the subjects and/or parents/legal guardians on Day 36 and Day 60 (See Section 6.4.5).

Japan participants who rolled over into study C3291027 without a Post Treatment Follow Up period prior to 21 Oct 2020 are considered completers in this study. A schematic of the study design is shown in Figure 1.

Figure 1. Study Design Schematic

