5.1. Allocation to Treatment

Allocation of subjects to treatment groups will proceed through the use of an interactive response technology (IRT) system (interactive Web-based response [IWR]). The site personnel (study coordinator or specified designee) will be required to enter or select information including but not limited to the user's identification (ID) and password, the protocol number, and the subject number. The site personnel will then be provided with a treatment assignment, randomization number, and dispensable unit (DU) or container number when investigational product is being supplied via the IRT system. The IRT system will provide a confirmation report containing the subject number, randomization number, and DU or container number assigned. The confirmation report must be stored in the site's files.

The study specific IRT reference manual will provide the contact information and further details on the use of the IRT system.

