6.2.1.1. Main Analysis

- Estimand strategy: Hypothetical.
- Analysis set: FAS.
- Analysis methodology: The percentage of subjects achieving Improvement in ISGA at Day 29 will be compared between crisaborole arm and vehicle arm and the difference will be tested based on normal approximation to response rates.
- Intercurrent events and missing data: Data after treatment discontinuation prior to Day 29 will not be considered. Missing ISGA scores will be derived for the analysis using MI-MCMC.
- Reporting results:
 - Tables: The sample size, number, percentage and 95% CI of percentage of subjects achieving Improvement in ISGA at Day 29 will be presented for each treatment. Risk difference and the corresponding 95% CI and p-value for the test of difference based on normal approximation to response rates will also be presented at Day 29.

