6.4. Subset Analyses

The main analysis of primary efficacy endpoint and key secondary efficacy endpoints will be repeated by subgroups defined through geographical regions, age groups (ages 2–11 years, ages 12–17 years, and ages 18 years and older), and baseline ISGA score (ISGA score 2, ISGA score 3). Subset analyses of these endpoints aim to evaluate the consistency of treatment effect across various subsets. P-values will not be reported here.

Summary of TEAEs and participant discontinuations due to AE will be reported by subgroups defined through geographical regions.

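### Neither protocol nor SAP specifies a stratification factor for the 2:1 allocation, so as written arm balance by age group, country and baseline ISGA is left to chance

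*Protocol*

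**What the plan says.** Protocol 4.3 describes the method in two sentences: "A centralized computer generated randomization schedule will be used to assign subjects to the treatment groups" and "Subjects will be randomized in a 2:1 ratio to one of the 2 parallel treatment groups". Protocol 5.1 runs allocation through an IRT system, where site staff enter "information including but not limited to the user's identification (ID) and password, the protocol number, and the subject number". That list is open-ended, and further detail is left to an IRT manual outside the documents. No block, minimisation rule or stratification factor appears in either document, and no redaction falls in 4.3 or 5.1.

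The plan nevertheless gives several baseline groups a role:

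- **Age 12.** Protocol 3 sets the enrolment target: "approximately 50% for age ≥ 12 years old and approximately 50% for age < 12 years old". In SAP 5.1 and 6.2.3 the last gate-kept endpoint, Week 4 Peak Pruritus NRS, is tested only in subjects aged 12 and over.
- **Country.** The trial is meant to support registration in China and Japan (Protocol 1.4.1).
- **Subgroups.** Under SAP 6.4 the main analyses of the primary and key secondary endpoints "will be repeated by subgroups defined through geographical regions, age groups" and baseline ISGA, without p-values. TEAEs and discontinuations due to AEs are also shown by region.

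The main analyses do not adjust for age or country. The MMRM carries treatment, visit, their interaction and the endpoint's own baseline value (SAP 6.1.1.1). For the ISGA rates, "the difference will be tested based on normal approximation to response rates" (SAP 6.2.1.1), with no covariate.

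**The concern.** All three factors are known before randomisation, and the plan singles them out, but nothing in the text holds the 2:1 ratio or the comparability of arms within them. Three things follow if allocation is in fact unstratified.

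- The NRS test rests on about half the subjects, and its arm ratio is not controlled.
- The two ISGA key secondaries are crude differences, so a chance imbalance in a prognostic factor passes straight into the estimate. Baseline ISGA is prognostic for Success by construction: a subject starting at 2 must reach 0 to gain two grades, while a subject starting at 3 needs 0 or 1. The Improvement threshold is a score of 0 or 1 whatever the baseline.
- Country tables for efficacy and safety may hold fewer vehicle subjects than 2:1 implies.

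At stake is precision and ease of interpretation in the one trial that is run, not the validity of the tests.

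**Working it through.** **Inputs from the documents.** Total 384, split 256:128; about 90% power for a 12-point difference at two-sided 0.05 (Protocol 9.1); about half aged 12 and over, taken as 192 (Protocol 3); earlier pooled ISGA response 32.1% and 21.8% (Protocol 9.1).

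**Plan's own figure.** The text after the significance level in 9.1 is redacted and no SD is visible, so the power cannot be reproduced independently. Solving back, SD = 12 / [√(1/128 + 1/256) × (1.960 + 1.282)] = 34.2. The stated power is consistent with an SD of about 34 before any dropout. Nothing below depends on it.

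**Arm ratio in the half aged 12 and over.** If allocation ignores age and arm totals are fixed, the number on vehicle, v, is hypergeometric (384 subjects, 128 on vehicle, 192 aged 12 and over).

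- Mean 192 × 128/384 = 64; SD 4.62; 95% range 55 to 73.
- Ratios at the ends: 137/55 = 2.49:1 and 119/73 = 1.63:1.
- Standard error relative to 128:64 is √{[1/v + 1/(192 − v)] / [1/64 + 1/128]}: 1.043 at v = 55 and 0.971 at v = 73.
- For an assumed standardised effect of 0.5, power is 0.88, 0.90 and 0.92 at v = 55, 64 and 73. For 0.4 it is 0.71, 0.74 and 0.77.

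**Difference between arms in the share aged 12 and over.** This is v/128 − (192 − v)/256 = (3v − 192)/256. Its SD is 3 × 4.62/256 = 5.4 points. It exceeds 10 points when v is 55 or less or 73 or more, with probability 0.066. It reaches 5 points with probability 0.33.

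**Country.** The split between China and Japan is not given. If one country supplied 30% of subjects (115, an assumption), its vehicle count would be 30 to 47 against 38 expected.

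**Effect on a crude ISGA difference.** Assume a factor held by 50% of subjects, with response rates 20 points apart between its levels. No figure in the documents supports the 20 points.

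- A 10-point imbalance moves the difference by 0.10 × 20 = 2 points.
- SE of the crude difference: √(0.321 × 0.679/256 + 0.218 × 0.782/128) = 4.67 points, so 2 points is 0.43 SE.
- Over all possible allocations, imbalance contributes an SD of 0.20 × 5.42 = 1.08 points, which is 1.08²/4.67² = 5.4% of the variance. Removing it would shorten the SE by 1 − √(1 − 0.054) = 2.7%.

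**What a cut at age 12 does not do.** For ages 12 to 17, with 48 subjects assumed, vehicle ranges over 10 to 22 (SD 3.06) without strata. With the half aged 12 and over held at 64 of 192, it ranges over 11 to 22 (SD 2.84), practically unchanged.

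**The case against.** Unstratified allocation at 384 subjects is a legitimate design. Chance imbalance is ordinary sampling error, already reflected in the confidence intervals; subgroup results carry no p-values; and the NRS comparison, made wholly within one age group, cannot be confounded by imbalance across age 12. All of this stands, and it is why the point is one of modest efficiency and clarity.

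It is also fair that the documents are silent rather than explicit. A reader might infer that subjects are drawn from a single unstratified list. The text does not support that: Protocol 4.3 says neither, the IRT entry list in 5.1 is expressly not exhaustive, and the IRT manual is not available. But if the IRT does stratify, the documents omit the factors and the analyses do not use them, so text is needed either way.

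Two further inferences would go too far. Baseline ISGA does not set the threshold for both ISGA endpoints, only for Success. And stratifying at age 12 would not repair the subgroup aged 12 to 17, or the quality-of-life instruments, whose age limits lie elsewhere (DLQI from 16, CDLQI 4 to 15, IDQOL 2 to 3, DFI 2 to 17; SAP 6.2.11).

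Timing is a real limit. Protocol 3 refers to Japanese participants who rolled over into an extension study before 21 October 2020, so enrolment was already under way at Amendment 3 (18 December 2020). Only later subjects could be stratified.

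**Conclusion.** The point holds as a gap in specification with a modest cost. No stratification factor is named for an allocation whose results are tested or read by age group, country and baseline ISGA. Randomisation remains valid and type I error is unaffected.

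The age figures assume 256:128, 192 subjects aged 12 and over, and allocation that ignores age. The country figure and the effect on the ISGA difference rest on assumed shares and an assumed prognostic gap; the documents give neither the country split nor the distribution of baseline ISGA. Improving this is worthwhile because it is cheap, not because the planned conclusions are at risk.

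**What to change.** **Allocation (Protocol 4.3 and 5.1).** State that, for all subjects randomised after the amendment, randomisation is stratified by age at consent (under 12; 12 and over) and country (China; Japan), 2:1 in permuted blocks within each stratum. List both values among the IRT entries. If the IRT already stratifies, name its factors instead.

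**Analysis (SAP 5.2, 6.1 and 6.2), fixed before unblinding.**

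- Add age group and country to the MMRM. For the NRS model only country applies, since age group is constant there.
- Replace the crude ISGA difference with a stratified or adjusted risk difference using age group, country and baseline ISGA (2, 3), computed in each imputed data set and combined as SAP 5.3 already plans. Without this, the standard error would not reflect the gain from stratified allocation.
- This part also covers subjects already randomised, and is the part that remains available if recruitment is complete.

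Both documents say that major changes to the primary analysis are also reflected in a protocol amendment, so the MMRM change belongs in the same amendment.

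**Cost.** IRT reconfiguration and amendment wording; incomplete blocks that may shift the overall ratio by a few subjects; and two allocation schemes to describe if introduced mid-trial. No extra subjects or visits.

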4.4. Lifestyle Requirements

4.4.1. Contraception

All female subjects who are of childbearing potential as applicable to the study who are, in the opinion of the investigator, sexually active and at risk for pregnancy with their partner(s) must agree to use an appropriate method of contraception consistently and correctly for the screening period, the duration of the active treatment period and for at least 28 days after the last dose of investigational product. The investigator or his or her designee, in consultation with the subject, will confirm that the subject has selected an appropriate method of contraception for the individual subject from the permitted list of contraception methods (see below) and will confirm that the subject has been instructed in its consistent and correct use. At time points indicated in the [Schedule of Activities](#), the investigator or his/her designee will inform the subject of the need to use an appropriate contraceptive method consistently and correctly and document the conversation and the subject’s affirmation in the subject’s

chart (subjects needs to affirm their consistent and correct use of at least 1 of the selected methods of contraception). In addition, the investigator or his/her designee will instruct the subject to call immediately if the selected contraception method is discontinued or if pregnancy is known or suspected in the subject or the partner.

Contraceptives allowed during the study include:

1. Established use of hormonal methods of contraception associated with inhibition of ovulation (eg, oral, inserted, injected, implanted, transdermal) provided the subject plans to remain on the same treatment throughout the entire study and has been using that hormonal contraceptive for an adequate period of time to ensure effectiveness.
2. Correctly placed copper containing intrauterine device (IUD).
3. Male condom or female condom used with or without a spermicide product (ie, foam, gel, film, cream, or suppository).
4. Male sterilization with absence of sperm in the post vasectomy ejaculate.
5. Bilateral tubal ligation/bilateral salpingectomy or bilateral tubal occlusive procedure (provided that occlusion has been confirmed in accordance with the device's label).

NOTE: Sexual abstinence, defined as completely and persistently refraining from all heterosexual intercourse (including during the entire period of risk associated with the study treatments) may obviate the need for contraception ONLY if this is the preferred and usual lifestyle of the subject.

4.4.2. Other Lifestyle Requirements

- Routine preventative immunizations are permitted during the study; however, it is preferred that immunizations be administered at least 28 days before the start or following the completion of the subject's participation.
- Subjects should not swim, be bathed or have treatment areas washed for at least 4 hours after application of investigational product.
- Use of sunscreen is permitted, but only on areas without AD involvement.

- The parent(s)/legal guardian should avoid wiping the investigational product off the skin and investigational product should not be reapplied to wiped areas until the next scheduled dose.
- When applying investigational product, the parent(s)/legal guardian will not be required to wear gloves when applying investigational product at home. However, they must be instructed to wash their hands with mild soap and water before and after each application.

4.5. Sponsor's Qualified Medical Personnel

The contact information for the sponsor's appropriately qualified medical personnel for the study is documented in the study contact list located in the supporting study documentation.

To facilitate access to appropriately qualified medical personnel on study related medical questions or problems, subjects are provided with a contact card. The contact card contains, at a minimum, protocol and investigational product identifiers, subject study numbers, contact information for the investigator site, and contact details for a contact center in the event that the investigator site staff cannot be reached to provide advice on a medical question or problem originating from another healthcare professional not involved in the subject's participation in the study. The contact number can also be used by investigator staff if they are seeking advice on medical questions or problems; however, it should be used only in the event that the established communication pathways between the investigator site and the study team are not available. It is therefore intended to augment, but not replace, the established communication pathways between the investigator site and the study team for advice on medical questions or problems that may arise during the study. The contact number is not intended for use by the subject directly, and if a subject calls that number, he or she will be directed back to the investigator site.

5. STUDY TREATMENTS

For the purposes of this study, and per International Conference on Harmonisation (ICH) guidelines, investigational product is defined as a pharmaceutical form of an active ingredient or placebo being tested or used as a reference/comparator in a clinical trial, including a product with a marketing authorization when used or assembled (formulated or packaged) in a way different from the approved form, or when used for an unapproved indication, or when used to gain further information about an approved use (ICH E6 1.33).

For this study, investigational products are the following:

- Crisaborole ointment, 2%, also referred to as active.

- Crisaborole placebo vehicle ointment, referred to as vehicle.

Crisaborole ointment, 2%, is formulated to contain PF-06930164 (2% wt/wt), white petrolatum, propylene glycol, mono and diglycerides, paraffin wax, butylated hydroxytoluene, and edetate calcium disodium.

Vehicle (no active drug in the formulation) contains white petrolatum, propylene glycol, mono- and diglycerides, paraffin wax, butylated hydroxytoluene, and edetate calcium disodium.

5.1. Allocation to Treatment

Allocation of subjects to treatment groups will proceed through the use of an interactive response technology (IRT) system (interactive Web-based response [IWR]). The site personnel (study coordinator or specified designee) will be required to enter or select information including but not limited to the user's identification (ID) and password, the protocol number, and the subject number. The site personnel will then be provided with a treatment assignment, randomization number, and dispensable unit (DU) or container number when investigational product is being supplied via the IRT system. The IRT system will provide a confirmation report containing the subject number, randomization number, and DU or container number assigned. The confirmation report must be stored in the site's files.

The study specific IRT reference manual will provide the contact information and further details on the use of the IRT system.

